10.7 Monitoring Plan for Death within 30 Days of Last Treatment

Each death on study not due to tumor will be reviewed by the NANT Study Management Committee, reported to NANT DSMB and a decision in consultation with NANT DSMB and IND sponsor will be made to close the trial, modify the trial, or continue unchanged; in addition, it will be determined if the event requires that new information be added to the informed consent. Each death occurring within 30 days of completing the last dose of MLN8237 regardless of cause will be reviewed and reported to the NANT DSMB and to the FDA according to standard procedure.

10.8 Pharmacokinetic and Correlative Biology Studies

Routine pharmacokinetic parameters for both MLN8237 and irinotecan will be determined using standard methods and reported descriptively. After completion of the phase II portion of the study, a final pharmacokinetic analysis will be performed that incorporates results from the phase I, phase II, and oral solution cohort portions of the study. Parameters to be determined include exposure, clearance, C_{max} , T_{max} , C_{ss} , and terminal half-life for both MLN8237 and irinotecan. These parameters will be assessed for both the enteric coated tablet formulation and for the oral solution formulation. These parameters will be qualitatively compared with estimates from prior studies of MLN8237 and irinotecan as single agents. In addition, these parameters for MLN8237 will be qualitatively compared between the enteric coated tablet and oral solution formulations.

The correlative biology studies are considered descriptive. For the study of *UGT1A1* genotype and toxicity, patients will first be categorized according to the number of *UGT1A1*28* alleles (0, 1, or 2 copies of the allele). Association between *UGT1A1* genotype and occurrence of (any) DLT and diarrhea will then be examined qualitatively. For the study of Aurora A expression, patients will first be categorized as having “high” or “low” Aurora A tumor expression for both mRNA and protein (using a median split). Association between Aurora A expression, response and EFS will then be examined. Similarly, associations between *MYCN* amplification status and Aurora A expression (mRNA and protein), response and EFS, and will be examined. These descriptive analyses will use contingency tables, scatterplots, and Kaplan-Meier plots, as well as corresponding quantitative measures of association. Association between *AURKA* genotype and objective response will be examined qualitatively. Patients will be categorized according to genotype at the two *AURKA* SNPs of interest (homozygous wild type; heterozygous; homozygous minor allele), with the percent of patients with at least a partial response or better given in each category.

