1.0 GOALS AND OBJECTIVES (SCIENTIFIC AIMS)

Primary Aims:

- 1.1 To estimate the maximum tolerated dose (MTD) of MLN8237 when given together with fixed doses of irinotecan and temozolomide in children and young adults with relapsed or refractory neuroblastoma.
- 1.2 To describe the toxicities of the combination of MLN8237, irinotecan, and temozolomide in children and young adults with relapsed or refractory neuroblastoma
- 1.3 To characterize the pharmacokinetics of irinotecan as well as MLN8237 enteric coated tablet and oral solution formulations in patients treated with this regimen
- 1.4 To determine the response rate for patients with relapsed or refractory neuroblastoma treated with MLN8237, irinotecan, and temozolomide at the identified MTD

Secondary Aim:

- 1.5 To determine the progression free survival rates for patients with relapsed or refractory neuroblastoma treated with MLN8237, irinotecan, and temozolomide at the identified MTD

Additional/Correlative Aims

- 1.6 To explore whether *MYCN* status and markers of expression of Aurora A in archival tumor tissue are associated with the antitumor activity of the combination of MLN8237, irinotecan, and temozolomide
- 1.7 To explore whether *UGT1A1* genotype is associated with toxicity in children with refractory neuroblastoma treated with the combination of MLN8237, irinotecan, and temozolomide
- 1.8 To explore whether *AURKA* genotype is associated with antitumor activity in children with refractory neuroblastoma treated with the combination of MLN8237, irinotecan, and temozolomide.

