2.8 UGT1A1 Polymorphisms and Irinotecan-Associated Toxicity

The active form of irinotecan is SN38. The UGT1A1 enzyme is thought to be the predominant enzyme involved in inactivating SN38 via glucuronidation. A growing body of literature has implicated polymorphisms in the promoter region of *UGT1A1* gene in inter-patient variability in irinotecan exposure and toxicity.[17] The *UGT1A1*28* allele leads to reduced expression of the gene and therefore diminished inactivation of SN38.[17] Several groups have demonstrated that adults who are homozygous for the *UGT1A1*28* allele have an increased risk of irinotecan-associated toxicity, particularly neutropenia.[17-20] Other groups have found that this effect is not seen with lower doses of irinotecan administered on a protracted schedule. [18-20]

MLN8237 also undergoes glucuronidation during its metabolism, which is partially mediated by *UGT1A1*. Therefore, genotyping of *UGT1A1* is of particular interest in this first study evaluating irinotecan used in combination with MLN8237. An optional correlative study will involve genotyping patients for *UGT1A1* promoter polymorphisms and correlating genotype with toxicity in patients receiving irinotecan and MLN8237.

Evaluation of Tissue Aurora A Expression

Increased tumor expression of Aurora A mRNA and protein has recently been shown to correlate with adverse prognostic factors and adverse outcome in patients with neuroblastoma.[12] It remains unclear whether Aurora A mRNA and/or protein expression will correlate with response to Aurora kinase inhibitors, such as MLN8237. An optional correlative study will involve evaluation of Aurora A expression in archival neuroblastoma tumor tissue for correlation with clinical response.

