2.12 Rationale for Amendment #5

Amendment #4 was an administrative amendment.

Amendment #5 designates the recommended phase 2 dose for this regimen when used with enteric coated tablets. After Amendment #3, dose levels 1B, 2B, and 3B were evaluated in the phase 1 portion of the study. At dose level 1B, 0 / 6 patients had first-course DLT. At dose level 2B, 1 / 6 patients had first-course DLT (prolonged grade 4 neutropenia). At dose level 3B, 2 / 4 evaluable patients had first-course DLT (prolonged grade 4 neutropenia; failure to meet platelet criteria by Day 35 of course 1). This experience established the recommended phase 2 dose as dose level 2B when used with MLN8237 enteric coated tablets. With Amendment 5, the phase 2 portion of the study is open to patients who are able to swallow intact pills. Patients on the phase 2 portion will begin therapy at dose level 2B and will utilize the enteric coated tablet formulation.

Amendment #5 also adds a cohort of patients treated with an MLN8237 oral solution. This new solution will provide access to patients who are unable to swallow intact pills. The pharmacokinetics of an oral solution formulation of MLN8237 was evaluated in 17 adult patients who participated in a cross-over relative bioavailability study evaluating both the powder-in-capsule formulation (with similar bioavailability to the current enteric coated tablet formulation) and the oral solution. The geometric mean ratios (oral solution in reference to the powder-in-capsule) for exposure (AUC_{inf}) and peak plasma concentration (C_{max}) were determined as 1.26 (90% CI 1.09-1.47) and 1.90 (1.52-2.37), respectively (Investigator Brochure). Based upon these results, pediatric patients receiving single-agent MLN8237 as the oral solution are recommended to receive $60 \text{ mg/m}^2/\text{dose}$ instead of the standard pediatric dose of 80 mg/m^2 obtained with intact pills. In the context of the current combination regimen in which the recommended phase 2 MLN8237 dose with enteric coated tablets is $60 \text{ mg/m}^2/\text{dose}$, patients in the oral solution cohort will begin therapy at dose level 1B with 45 mg/m^2 MLN8237. Patients in this cohort will exclusively receive the oral solution and will be required to participate in pharmacokinetic testing.

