2.13 Rationale for Amendment #6

Experience with this regimen prior to Amendment #6 has demonstrated that hematologic toxicity is the primary dose-limiting toxicity (DLT). However, some DLTs have been uncomplicated grade 4 neutropenia for > 1 week (to date, one episode in course 1 in the phase II portion in the absence of other DLT) or uncomplicated thrombocytopenia requiring platelet transfusions more than twice in a 1 week period (to date, one episode in course 1 in the phase II portion in the absence of other DLT). Having grade 4 neutropenia for > 1 week or need for multiple platelet transfusions during a nadir is consistent with the degree of hematologic toxicity seen in other common regimens used for patients with newly diagnosed high-risk neuroblastoma and in some regimens used in patients with relapsed disease. Therefore, with Amendment #6, these elements of the definition of hematologic DLT are removed. Hematologic DLT will be defined solely on the basis of delays in starting subsequent courses beyond day 36 due to failure to recover counts. Day 36 has been updated from Day 35, as that would be a true two week delay, and allowing for patients to stay on a Monday start schedule.

Prior to Amendment #6, the statistical design allowed up to 6 patients from the phase I portion of the trial to contribute to the phase II portion of the trial. Given early evidence of activity of this regimen, there is a desire to complete a full independent phase II evaluation of this regimen. Amendment #6 formally separates the phase I and phase II portions of the study and will require an additional 6 patients evaluable for response. Patient accrual to the phase II portion has been rapid, such that enrolling an additional 6 patients is feasible.

Amendment #6 also updates eligibility and response criteria for uniformity with other current active NANT clinical trials. The consent form and drug information section have been updated to include updated risk tables based upon the most recent MLN8237 Investigators Brochure. Additional minor edits are also included.

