3.2.10 Organ Function Requirements

3.2.10.1 Hematologic Function:

Patients must meet the following hematologic criteria for enrollment onto the oral solution cohort of the study regardless of bone marrow disease status:

- a. ANC: $\geq 1000/\mu\text{L}$ (no hematopoietic growth factors within 7 days of the start date of protocol therapy); and
- b. Platelet count: $\geq 100,000/\mu\text{l}$, transfusion independent (no platelet transfusions within 1 week of the start date of protocol therapy).

Patients with bone marrow disease who meet the above count criteria will be eligible to enroll in the oral solution cohort of the study and will be evaluable for hematologic toxicity.

Patients must meet the following hematologic criteria for enrollment onto the phase 2 portion of the study unless they have bone marrow disease:

- a. ANC: $\geq 1000/\mu\text{L}$ (no hematopoietic growth factors within 7 days of the start date of protocol therapy); and
- b. Platelet count: $\geq 100,000/\mu\text{l}$, transfusion independent (no platelet transfusions within 1 week of the start date of protocol therapy).

Patients with bone marrow involvement on the phase 2 portion of the study must meet the following hematologic criteria. These patients will not be evaluable for hematologic toxicity or hematologic DLT:

- a. ANC $\geq 750/\mu\text{L}$ (no hematopoietic growth factors within 7 days of the start date of protocol therapy); and
- b. Platelet count $\geq 50,000/\mu\text{L}$ (platelet transfusions allowed).

3.2.10.2 Renal Function:

Patients must have adequate renal function defined as age-adjusted serum creatinine $\leq 1.5 \times$ normal for age (see below):

Age	Maximum Allowable Serum Creatinine
≤ 5 years	0.8 mg/dL
> 5 and ≤ 10 years	1.0 mg/dL
> 10 and ≤ 15 years	1.2 mg/dL
> 15 years	1.5 mg/dL

3.2.10.3 Liver Function:

- a. Total bilirubin $\leq 1.5 \times$ normal for age;
- b. SGPT (ALT) ≤ 135 U/L ($\leq 3 \times$ ULN) for the oral solution cohort and ≤ 225 ($\leq 5 \times$ ULN) for the phase 2 portion of the study. Note that for ALT, the upper limit of normal for all sites is defined as 45 U/L.

3.2.10.4 Reproductive Function:

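### The descriptive UGT1A1 analysis omits neutropenia, the toxicity its rationale stresses, and relies on an any-DLT outcome whose neutropenia content changed at Amendment 6

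*Combined protocol and SAP*

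**What the plan says.** Aim 1.7 in Section 1.0 asks whether UGT1A1 "genotype is associated with toxicity in children with refractory neuroblastoma" treated with the combination. The aim speaks of toxicity in general.

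Section 2.8 gives the reason for the substudy: adults homozygous for the \*28 allele "have an increased risk of irinotecan-associated toxicity, particularly neutropenia". The same paragraph then limits this: "Other groups have found that this effect is not seen with lower doses of irinotecan administered on a protracted schedule".

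Section 10.8 sets the analysis. "The correlative biology studies are considered descriptive", patients are grouped by 0, 1 or 2 copies of \*28, and the association between UGT1A1 "genotype and occurrence of (any) DLT and diarrhea will then be examined qualitatively". No other UGT1A1 outcome is named.

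Three other places determine what any DLT can capture:

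- Section 2.13 (Amendment 6): "Hematologic DLT will be defined solely on the basis of delays in starting subsequent courses beyond day 36 due to failure to recover counts". Grade 4 neutropenia lasting more than a week is no longer a DLT in itself. Section 4.4 matches this.
- Section 4.4 also says that the new definition takes effect at each site on IRB approval, for new toxicities in patients already on therapy.
- Section 3.2.10.1, on phase 2 patients with marrow involvement who enter under the lower count criteria: "These patients will not be evaluable for hematologic toxicity or hematologic DLT". Section 10.4 confirms that this status is kept even if the marrow improves.

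**The concern.** The outcome set does not fit the question. The rationale points to neutropenia, the plan lists any DLT and diarrhea, and the DLT outcome now registers neutropenia only as a failure to recover counts by day 36. Two patients with the same prolonged grade 4 neutropenia, one before Amendment 6 and one after, can fall in different cells of the genotype table for a reason unrelated to genotype.

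At stake is Aim 1.7. Followed as written, the substudy could report no visible association between UGT1A1 genotype and toxicity without having looked at neutropenia by genotype. The protocol itself expects myelosuppression to be the main toxicity (second hypothesis in the synopsis), and Section 2.13 calls hematologic toxicity the primary dose-limiting one.

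**Working it through.** Section 10.8 states no sample size, error rate or effect size for this analysis, so there is no planned figure to reproduce. The check sets the sections side by side, then uses the phase 1 DLT counts to show how far the definition moves the outcome.

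**Is neutropenia related to genotype anywhere?**

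- Section 10.8, UGT1A1: any DLT and diarrhea only.
- Section 10.6.1: all toxicities tabulated by formulation, dose level and course, with emphasis on diarrhea, mucositis and myelosuppression. Genotype is not a table dimension.

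Neutropenia is therefore reported, but not by genotype. It reaches the genotype table only through any DLT.

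**How much does the DLT definition matter?** First-course DLTs in phase 1, from Sections 2.11 and 2.12:

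| Dose level | DLT / patients | Description |
|---|---|---|
| 1 | 2/6 | one with mucositis, prolonged grade 4 neutropenia and platelet delay; one with neutropenia delay |
| 1B | 0/6 | none |
| 2B | 1/6 | prolonged grade 4 neutropenia |
| 3B | 2/4 | prolonged grade 4 neutropenia; platelet criteria unmet by day 35 |

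For level 2B the text is "1 / 6 patients had first-course DLT (prolonged grade 4 neutropenia", with no other component listed.

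- As reported: 2 + 0 + 1 + 2 = 5, over 6 + 6 + 6 + 4 = 22. The denominator matches the 22 phase 1 patients in Section 10.1. 5/22 = 22.7%.
- Under the Amendment 6 definition, without the two cases described only as prolonged grade 4 neutropenia (one at 2B, one at 3B): 5 − 2 = 3, so 3/22 = 13.6%.
- If the 3B neutropenia case also had a qualifying delay: 4/22 = 18.2%.
- B levels only (6 + 6 + 4 = 16): 3/16 = 18.8% becomes 1/16 = 6.3%, or 2/16 = 12.5% under that alternative.

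Four of the five DLT patients had a neutropenia component (two at level 1, one at 2B, one at 3B). Under Amendment 6, only the level 1 neutropenia delay would still be a DLT because of neutropenia. Section 2.13 adds one phase 2 course 1 patient whose only DLT was grade 4 neutropenia for over a week.

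**Limits of this illustration.** It assumes that the two delay-only cases (neutropenia at level 1, platelets at 3B) also ran past day 36, and that the two 3B descriptions belong to one patient each. It counts all phase 1 patients, because the number genotyped is not given. It covers first-course events, whereas Section 10.8 sets no course limit on any DLT.

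**The case against.** The best defense is that this is an optional, exploratory aim with a qualitative analysis, and that no dose decision, stopping rule or primary conclusion depends on it. That stands, and it sets the weight of the point. It does not justify leaving out the outcome that the rationale stresses, since a descriptive table still has to show the right quantity.

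A second defense is that Section 2.8 rests on adult data and carries its own caveat about lower, protracted dosing. That also stands: the documents do not establish the neutropenia effect for this regimen, nor say on which side 50 mg/m²/day for 5 days falls. This is a reason to look rather than to omit.

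A third is that neutropenia is itself altered by supportive care. Growth factor from day 8 is mandatory at the B levels (Section 4.2.4), MLN8237 is myelosuppressive and its dose varies, and twice-weekly counts can miss the true nadir. All of this is fair and shapes the fix. Prolonged grade 4 neutropenia nevertheless occurred at 2B and 3B with growth factor required.

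A reader might infer more than the documents support:

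- *That Section 10.8 runs a hypothesis test.* It does not; the examination is qualitative.
- *That Amendment 6 took neutropenia out of the DLT definition.* Failure to meet neutrophil criteria by day 36 still counts.
- *That earlier DLTs were reclassified.* Section 4.4 applies the new definition to new toxicities; nothing says that recorded events were changed.
- *That hematologically inevaluable patients create false zeros.* They would only if tabulated as having no DLT, and Section 10.8 does not say how they are shown.
- *That neutrophil data go unused.* Section 10.6.1 reports them, only not by genotype.
- *That neutropenia is the more informative outcome because the earlier cooperative-group study had 25% with grade 3 or higher neutropenia, against under 5% for grade 3 or 4 diarrhea in the studies cited in Section 2.2.* Those patients received no MLN8237, and the irinotecan schedule in that study differed. In this trial, 3 of 6 patients at dose level 1 had grade 3 diarrhea (Section 2.11).

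**Conclusion.** The point holds as a gap in a descriptive analysis. No planned analysis relates UGT1A1 genotype to neutropenia itself, and the DLT outcome that might stand in for it mixes two definitions. In phase 1 the choice of definition moves the first-course DLT count from 5/22 to 3/22, or 4/22 under the alternative. The size rests on the brief descriptions in Sections 2.11 and 2.12, which do not say whether the prolonged-neutropenia cases also missed count recovery. If both had, the count would stay at 5/22. The absence of a genotype-by-neutropenia table does not depend on that. The consequence is confined to Aim 1.7; the MTD, response and toxicity conclusions are unaffected.

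**What to change.** In Section 10.8:

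1. Add cycle 1 neutropenia by CTCAE grade, including grade 4, as a descriptive UGT1A1 outcome, tabulated by 0, 1 or 2 \*28 alleles. The source is the twice-weekly cycle 1 blood counts in Section 7.1.
2. Restrict hematologic outcomes to patients evaluable for hematologic toxicity, which excludes phase 2 patients with marrow involvement who entered with low baseline counts.
3. Apply one named DLT definition to all genotyped patients for this analysis. This concerns the table only and changes no DLT recorded for dose decisions.
4. Show dose level 1 separately from the B levels, because both growth factor and cephalosporin prophylaxis became mandatory at the latter, and show MLN8237 dose level.

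ANC nadir or an allele-trend estimate with a confidence interval is optional.

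The cost is a few lines of text and one table, with no new samples. The downside is a smaller n for hematologic outcomes, by a number the documents do not give, and imprecise estimates in every genotype cell.

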10.9 Inclusion of Women and Minorities

The study is open to all participants regardless of gender or ethnicity. Review of accrual to past NANT studies of new agents demonstrates the accrual of both genders and all NIH-identified ethnicities to such studies. The small number of patients entered into this trial will obviate any analysis of variation in response rate with gender or ethnicity.

11.0 RESPONSE CRITERIA VERSION 1.2

With Amendment #6, response criteria have changed to the following NANT Response Criteria version 1.2. The previous NANT Response Criteria versions 1.0 and 1.1 have been moved to Appendix VII and Appendix VIII, respectively, for reference. For all patients enrolling prior to Amendment #5, sites should continue to utilize version 1.0 to assess and report response. For all patients enrolling with Amendment #5 and after, sites will use version 1.2 to assess and report response. NANT central review of response will utilize version 1.2 for all patients.

Overall response will incorporate all three parameters: CT/MRI; MIBG (FDG-PET is substituted for MIBG non-avid tumors); and bone marrow response with response defined as outlined in Section 11.6. Response for each parameter and overall response will be reported by the treating site using the criteria below. However, the final statistical analysis of response will be defined by central review, using the same criteria below.

11.1 Response Criteria for CT/MRI Lesions

For lesions evaluated by CT/MRI, this study will use the definitions of measurable disease from the Response Evaluation Criteria in Solid Tumors (RECIST 1.1; European Journal Cancer 45: 228-247, 2009) modified per the criteria below to define target lesions (lesions which are measurable AND evaluable for response).

11.1.1 Definition of soft tissue TARGET LESIONS on CT/MRI:

Soft tissue target lesions that will be followed for response must meet criteria in a. and b. below:

- a. A target lesion must be measurable, defined as a soft tissue lesion that can be accurately measured in at least one dimension with a longest diameter $\geq 10\text{mm}$, or for lymph nodes $\geq 15\text{mm}$ on short axis. (The short axis is measured after identifying the longest diameter of a lymph node or nodal mass, and then measuring the longest perpendicular diameter to that as the short axis).
- b. A target lesion must also be evaluable for response: To be evaluable, the lesion must also be MIBG or FDG-PET avid (if tumor known to be MIBG non-avid), or have a biopsy as required in the eligibility criteria. If one soft tissue lesion present at enrollment is biopsied showing neuroblastoma or ganglioneuroblastoma at any time point, then all other soft tissue lesions present at enrollment are considered evaluable. Bone marrow positivity does not affect soft tissue evaluability.

NOTE: Soft tissue components of bone lesions will be considered measurable lesions if $> 10\text{mm}$ in at least one dimension, and evaluable for response if MIBG avid (or FDG-PET-avid if tumor known to be MIBG non-avid).

Serial measurements of target lesions are to be done with the same method of assessment (either CT or MRI) used to characterize each lesion reported at baseline. The sum of diameters (longest for non-nodal lesions, short axis for nodal lesions) for all target lesions will be calculated and reported as the **sum of diameters**.

11.1.2 NON-TARGET SOFT TISSUE LESIONS will include:

- a. Leptomeningeal tumor and tumor in cerebrospinal fluid cytology will be considered non-target lesions.
- b. Lesions that are considered likely to be active tumor by the treating physician based on clinical correlation (for example, hepatic and pulmonary nodules)

11.1.3 The following lesions will NOT be followed to evaluate response either as target lesions or non-target lesions, if they meet the criteria below **AND** the treating physician feels they are unlikely to represent active tumor (an exception for active tumor will be made for c. below):

- a. Measurable soft tissue lesions ($\geq 10\text{mm}$) that are not MIBG avid or PET avid (if tumor known to be MIBG non-avid) and if biopsied did not show neuroblastoma or ganglioneuroblastoma.

- b. Non-measurable soft tissue lesions < 10mm or non-measurable lymph nodes (defined as lymph nodes >10 to <15mm on short axis).
- c. Intramedullary bone lesions will not be followed for CT/MRI response even though they are felt to represent active tumor since they will be evaluated with MIBG scans (or FDG-PET scans if MIBG non-avid), and since bone changes on CT/MRI are known to persist after resolution of active tumor.

11.1.4 The response of the CT/MRI lesions will be defined as outlined below:

